Cover Page:

Study Protocol

Title of the study:

A Risky Sex Prevention Intervention for Middle School Age Minority Girls

NCT number:

NCT02103218

Date of the document:

January 28, 2019

The study objectives were to address the following research questions (RQs):

RQ1. What is the efficacy of the intervention in delaying initiation of sex or reducing risky sex behaviors by young Black girls?

RQ2. Does the intervention produce changes in black middle school girls' knowledge of HIV, communication with mothers (including bonding and monitoring), self-esteem, racial pride, empowerment and sexual assertiveness?

RQ3. Does the intervention produce changes in mothers' mother-daughter communication, bonding, and maternal monitoring?

Study design

A quasi-experimental, longitudinal design was used to test the efficacy of a family-level HIV preventive intervention for young Black girls relative to girls in a comparison group to assess HIV knowledge, communication and bonds with their mothers, racial/ethnic pride, self-esteem, and assertiveness and to empower girls. Data were collected for all participants at baseline (prior to the intervention), immediately post-intervention (three months post-baseline), and at three- and nine-month follow-up.

The study statistical analysis plan is uploaded as a separate document to clinicaltrials.gov.

Cover Page:

Statistical Analysis Plan

Title of the study:

A Risky Sex Prevention Intervention for Middle School Age Minority Girls

NCT number:

NCT02103218

Date of the document:

January 27, 2019

Statistical Analysis Plan

The study was powered to detect a 0.24 proportion difference in prevalence of risky sexual behavior with 80% power assuming a 0.05 significance level when the sample size was 40 girls per group at study's end. Also, the study was powered to detect an increase of 9 points on HIV knowledge, an increase of 3 points on self-esteem, an increase of 0.26 in racial pride, and an increase of 0.52 in assertiveness under similar assumptions.

Baseline characteristics were compared between intervention groups using *t*-tests or Wilcoxon rank-sum tests for continuous characteristics and Chi-square or Fisher's exact tests for categorical measures. Analyses were performed separately for girls and mothers. Attrition rates across study follow-up were compared between groups using Chi-square tests. Multiple imputation for missing data was performed in sensitivity analyses with 20 imputations using predictive mean matching with a fully conditional specification method (Berglund, 2014).

Inverse probability weighting (IPW) using propensity scores were used to account for the quasi-experimental study design (Austin, 2015; Stuart, 2007). The goal of such weighting is to balance the distribution of variables that would approximate balance as if a randomized controlled trial had been performed. Propensity scores were first estimated using pre-intervention baseline measures related to outcomes, as recommended by Brookhart (2006) and current literature. Standardized differences were compared before and after weighting for assessing whether adequate balance had been achieved (Austin & Stuart, 2015) as well as sensitivity analyses incorporating IPW and without were performed. Robust sandwich standard errors were additionally specified to account for propensity score estimation (Joffe, 2012).

Longitudinal comparisons of change over time between groups were performed using generalized estimating equations modeling (GEE; Fitzmaurice, Laird, & Ware, 2011). Outcomes

exhibiting skewness or suggestion of non-Normality were modeled using negative binomial count GEE. Model-based time-point specific differences were interpreted if omnibus tests for any differences in change over time between groups (i.e., group by time interaction) were significant (Fitzmaurice et al., 2011). A two-sided p -value < 0.05 was considered statistically significant.

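### Does the unstated working correlation leave the main GEE open to bias from dropout that differs by group?

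*SAP*

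**What the plan says.** The SAP's final paragraph gives the main method: "Longitudinal comparisons of change over time between groups were performed using generalized estimating equations modeling". Skewed outcomes get a negative binomial version. Follow-up contrasts are gated: "Model-based time-point specific differences were interpreted if omnibus tests for any differences in change over time between groups" reach significance. No working correlation is named for either model.

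Three other statements bear on dropout:
- Second paragraph, imputation: "Multiple imputation for missing data was performed in sensitivity analyses with 20 imputations using predictive mean matching". The main GEE is therefore read as using the visits each participant completed.
- Second paragraph, attrition: "Attrition rates across study follow-up were compared between groups using Chi-square tests".
- Third paragraph, weighting: "Inverse probability weighting (IPW) using propensity scores were used to account for the quasi-experimental study design". "Propensity scores were first estimated using pre-intervention baseline measures related to outcomes", and "Robust sandwich standard errors were additionally specified to account for propensity score estimation".

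The Protocol describes a non-randomised design with four visits: baseline, the end of the intervention, and two later follow-ups.

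**The concern.** The working correlation is usually a matter of efficiency, but with incomplete follow-up it also affects bias. Under independence with a saturated group-by-time mean, each fitted value is the weighted mean of those still present. If leaving depends on earlier answers, that mean drifts. If it drifts differently in the two groups, the interaction drifts too.

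Nothing stated for the main model clearly prevents this. The propensity weights balance group membership at baseline and cannot follow answers given later. Sandwich errors change the variance, not the estimate. The chi-square test sees how many leave, not who leaves.

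The interaction test decides whether any time-point difference is interpreted, so both the gate and the estimates behind it could be affected, including the sexual-behaviour outcome of the Protocol's RQ1. Different dropout mechanisms are plausible because the groups were not randomised and only one received the intervention.

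**Working it through.** **The plan's own figure.** The SAP states that the study was "powered to detect a 0.24 proportion difference in prevalence of risky sexual behavior with 80% power assuming a 0.05 significance level", with 40 per group at the end. It gives no prevalences. The pooled two-proportion formula is n = [1.96√(2p̄q̄) + 0.842√(p₁q₁ + p₂q₂)]² / d². Take p₁ = 0.066, p₂ = 0.306, d = 0.24, p̄ = 0.186:
- 2p̄q̄ = 0.3028, root 0.5503, times 1.96 = 1.079
- p₁q₁ + p₂q₂ = 0.0616 + 0.2124 = 0.2740, root 0.5235, times 0.842 = 0.441
- n = (1.079 + 0.441)² / 0.0576 ≈ 40

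The figure is attainable at a low prevalence. For a continuous outcome, 40 per group detects (1.96 + 0.842) × √(2/40) ≈ 0.63 SD. These are the yardsticks for the biases below.

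**Direction of the bias.** Under independence, bias in group g at visit t = E(Yₜ | still present, g) − E(Yₜ | g). The contrast carries the difference between the two groups' biases, which largely cancels when the mechanism is shared.

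**Size at trial scale.** All inputs are assumed, since the SAP gives no dropout rate or correlation: 53 per group, 25% loss in each (53 × 0.75 ≈ 40 left), no true effect, baseline difference 0.3 SD, estimated propensity weights, visits at 0, 3, 6 and 12 months, and dropout logistic in the previous score. Several correlation structures (exchangeable 0.5 and 0.7, and decaying) give the ranges. Bias is absolute, for baseline to the last visit. Rejection is for the omnibus test at nominal 5%.

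| Dropout mechanism | Independence: bias; rejection | Exchangeable: bias | By-group PMM imputation: bias |
|---|---|---|---|
| Shared (slope 1 per SD) | 0.02–0.03 SD; 0.043–0.053 | – | – |
| One group only, slope 0.5 | 0.06–0.09 SD; 0.054–0.070 | 0.00–0.03 SD | – |
| One group only, slope 1 | 0.11–0.15 SD; 0.058–0.092 | 0.00–0.03 SD | 0.02–0.03 SD |
| Opposite slopes (extreme) | 0.23–0.31 SD; 0.098–0.248 | 0.01–0.05 SD | 0.05–0.07 SD |

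Exchangeable rejection was 0.043 to 0.059 throughout. Without propensity weights, independence at slope 1 in one group gave 0.12 to 0.17 SD.

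**A second simulation with other inputs.** With large samples, weights and one-group slope 1, independence was off by 0.10 SD (20% loss, correlation 0.5) up to 0.20 SD (30% loss, correlation 0.7). With 50 per group, 20% loss and correlation 0.5, the omnibus test rejected as follows:
- Random dropout: 5.7%.
- One-group dropout: 8.2% under independence, 7.4% under exchangeable.
- Opposite slopes: 12.5% under independence, 6.8% under exchangeable.

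With 1,000 replicates, the SE of the one-group gap, treated as unpaired, is √(0.082×0.918/1000 + 0.074×0.926/1000) ≈ 0.012. The gap of 0.008 is thus within noise. The attrition chi-square rejected 4% to 6% of the time, so it does not detect the problem.

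**Binary outcome** (25% loss, no propensity weights, logit link assumed). Independence moved the last-visit difference as follows:
- One group only: 1.0 to 3.0 points when a previous yes doubles the odds of leaving, 2.4 to 6.1 points at odds ratio 4.
- Shared mechanism: 0.1 points or less.

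Exchangeable moved it by at most 1.1 points for one group and 1.8 for opposite mechanisms. The planned difference is 24 points. At an assumed prevalence of 0.20 and 20% to 30% loss, the second simulation gave 3 to 11 points under independence, the upper end needing opposite slopes.

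**The planned imputation.** Ordinary pooled PMM with a group term and earlier visits (unweighted, no true effect, 5 imputations) left 0.013 to 0.025 SD for one-group dropout and 0.025 to 0.030 SD for opposite slopes. Independence gave 0.12 to 0.17 and 0.24 to 0.33 SD in the same setting. Separate imputation models by group are not needed for most of the protection.

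**The case for a change.** The strongest case for acting is that the unstated choice decides whether the main result is largely protected or exposed, that a reader cannot tell which was run, and that one sentence would settle it. The first two points stand as a description of the document. The mechanism is also sound: wherever dropout slopes differed by group, independence was biased, and the propensity weights did not remove the bias.

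Two further points stand in part. The SAP does not list the imputation variables or say how a disagreement with the main result would be read. And exchangeable is not a complete cure: some bias remains when correlation decays over time, and its protection is less assured for the binary and negative binomial outcomes.

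What does not follow is that the plan contains an error. No passage says independence was used, and none suggests that dropout mechanisms differed. The largest figures need opposite mechanisms in the two groups.

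The heavier remedies have their own costs. Weights for remaining in the study would rest on about 13 dropouts per group (53 × 0.25) and raise the SD of the contrast by up to 21%. A dropout model by group detects a one-group slope of 0.5 only about 21% of the time, and a slope of 1 about 60%. The SAP is written in the past tense, so a new main analysis would probably be post hoc.

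**Conclusion.** No change to the plan follows. The missing working correlation and missingness assumption are detail that an analyst fills sensibly. With a common non-independence structure, bias under one-group dropout is 0.03 SD or less for continuous outcomes and about one percentage point or less for the binary one. The imputation already planned gives a cross-check of similar quality, provided earlier visits enter it, which is the natural reading of a chained imputation of longitudinal data.

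The exposed case needs independence and group-specific dropout together. Even then, at 25% loss, one-group dropout gives about 0.06 to 0.17 SD against a detectable 0.63 SD, and 1 to 6 points against a planned 24. Choosing between exchangeable GEE and dropout weights is a trade-off of bias against precision.

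All these sizes rest on assumed dropout rates, slopes and correlations. The actual size cannot be known from the documents.

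### The SAP says its sandwich standard errors account for propensity score estimation; the usual weighted-GEE sandwich does not, and the direction of the error depends on choices the SAP leaves unstated

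*SAP*

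**What the plan says.** The third paragraph of the SAP sets out the weighting: "Inverse probability weighting (IPW) using propensity scores were used to account for the quasi-experimental study design". Its aim is given as "The goal of such weighting is to balance the distribution of variables that would approximate balance as if a randomized controlled trial had been performed". On the score model, "Propensity scores were first estimated using pre-intervention baseline measures related to outcomes". On checking, "Standardized differences were compared before and after weighting for assessing whether adequate balance had been achieved", and "sensitivity analyses incorporating IPW and without were performed". On variance, the only statement is "Robust sandwich standard errors were additionally specified to account for propensity score estimation", with a citation.

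The fourth paragraph analyses change over time between groups by GEE, with skewed outcomes "modeled using negative binomial count GEE". Time-point differences are interpreted only when the omnibus group-by-time test is significant at two-sided 0.05. The first paragraph plans on a "sample size was 40 girls per group" at study end. The Protocol (Study design) gives four visits.

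Not stated: the kind of sandwich, whether weights target the ATE or the effect in the treated (ATT), the covariates in the score, whether each outcome's own baseline value is among them, and whether the omnibus test is weighted.

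**The concern.** A robust sandwich on a weighted GEE allows for within-person correlation and for unequal weights. It does not know that the weights came from a fitted model. Uncertainty from that fit enters the variance only if the propensity equations are stacked with the outcome equations, or if a bootstrap refits the score in every resample. The SAP mentions neither, yet tells the reader that the matter has been dealt with.

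Weighting is the SAP's adjustment for the lack of randomization, so the weighted intervals are the ones meant to carry a causal reading. If their standard errors are wrong, precision is misstated in a small study, and a reader cannot tell from the SAP in which direction.

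**Working it through.** **Inputs.** From the documents: 40 per group (N = 80), four visits, GEE, two-sided 0.05, score fitted on outcome-related baseline measures. Everything else is assumed: weight type, 3 to 8 covariates, selection strength (c-statistic 0.61 mild, 0.70 moderate), visit correlation 0.4 to 0.8, outcome prevalence and analysed N. The SAP gives no standard error or coverage figure to reproduce. Its 0.24 detectable difference is attainable (0.06 against 0.30 gives power 0.81 at 40 per group) but depends on a prevalence that is not given; this point does not rest on it.

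**Step 1: the two variances.** Let D be change from baseline, A the group, p the fitted score and w = A/p + (1−A)/(1−p), the ATE weight. W1 and W0 are the sums of weights in each group, and m1 and m0 the weighted mean changes. Each participant contributes

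φ = wA(D−m1)/W1 − w(1−A)(D−m0)/W0.

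The usual sandwich reports SE² = Σφ². With estimated weights the contribution is ψ = φ + G′I⁻¹s, where s is the participant's propensity score equation, I its information matrix and G the derivative of the contrast with respect to the propensity coefficients. The usual sandwich leaves out the second term. With ATE weights and a correct score model, that term removes from φ the part explained by s, so the true variance cannot exceed the reported one in large samples.

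**Step 2: when the omitted term matters.** G is driven by how well the score's covariates predict D. With no selection, equal groups and large N, reported SE / true SD = 1/√(1−R²), where R² is the share of variance in D that those covariates explain. The simulated settings with the baseline outcome in the score have R² of about 0.36, 0.27 and 0.15 at visit correlations 0.4, 0.6 and 0.8:

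- 1/√0.64 = 1.25
- 1/√0.73 = 1.17
- 1/√0.85 = 1.08

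If the baseline outcome is left out and the covariates shift all visits equally, they cancel from D. Then R² = 0 and the ratio is 1.

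**Step 3: simulation at N = 80.** ATE weights, mild or moderate selection, no true effect, usual sandwich, baseline-to-last-visit change:

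| Score contains | SE / true SD | Single-contrast error | Omnibus error |
|---|---|---|---|
| Baseline outcome (24 runs: normal, negative binomial, binary, dropout) | 1.01–1.21 | 2.1–5.0% | 4.5–7.9% |
| No baseline outcome; covariate effects constant, normal | 0.93–1.00 | 4.9–7.1% | 6.9–9.3% |
| No baseline outcome; covariates predict change | 0.96–1.21 | – | – |

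In the first row, correlation 0.4 gives 1.13–1.21, 0.6 gives 1.07–1.13 and 0.8 gives 1.01–1.05 (normal outcome). These are the Step 2 values, lowered by selection and by the sandwich's small-sample bias. Separate runs with other covariate strengths, also with the baseline outcome in the score, reached 1.41.

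**Step 4: large samples.** At N = 2000 the ratio was 1.18–1.24 with the baseline outcome in the score, and 0.98–1.04 without it and with constant covariate effects. The excess therefore persists in the first case and is absent in the second.

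**Step 5: alternatives at N = 80.** A bootstrap refitting the score gave 0.99–1.08 in the 24 runs of the first row, and 0.95–1.04 in five further settings run to test the dependence on score content. Referred to F, its omnibus test ran at 4.3–6.7% in the 24 runs. An uncorrected stacked sandwich gave 0.86–0.95, with omnibus error 8.4–15.0%.

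**Step 6: balance.** With the baseline outcome in the score, replicates in which every weighted standardized difference was below 0.10 still had ratios of 1.03–1.24 (normal outcome). The planned balance check does not detect or remove the error.

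**The case against.** The strongest reply has three parts.

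**The SAP never says which sandwich was used.** A stacked sandwich is also a robust sandwich, and the cited source may describe one. This stands in part. A reader might infer that the plain version was certainly used; the text does not establish that. But a stated property with no described method that would deliver it is a defect either way, and the uncorrected stacked version performs poorly at this sample size.

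**The direction is not fixed.** A reader might infer that weighted intervals are typically too wide and that power is lost. That needs the baseline outcome, or covariates predicting change, in the score. The SAP says only that the measures are related to outcomes, and a covariate can be related to an outcome at every visit without predicting its change. This stands, and it also limits the claim about large samples.

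**The practical gain may be small.** At visit correlation 0.8 the bootstrap brought no power gain. At N = 60 it lost power on the single contrast (65.9% against 70.8%). At correlation 0.4, for an assumed effect of 0.634 SD, omnibus power was 80.4–91.3% with the bootstrap against 74.1–78.6% with the usual sandwich. A gain is possible, not something to expect.

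Binary outcomes show the same dependence: 1.15–1.20 for change with baseline in the score, but 0.95–1.11 for a last-visit difference without it.

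**Conclusion.** The point holds in conditional form. The statement on standard errors is wrong for the usual weighted-GEE sandwich and unsupported for any other, because no method that carries score estimation into the variance is described.

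At 40 per group with ATE weights, the standard error is about 1.0 to 1.2 times the true value if the score contains the baseline outcome or covariates that predict change, and about 0.93 to 1.0 if it contains neither. In the second case the shortfall is small-sample bias of the sandwich, not neglect of score estimation. The omnibus test ranged from 4.5% to 9.3% across the two main cases, so it can be mildly liberal in either; it should not be called conservative because some intervals are wide. A reader might also infer general false-positive inflation. The larger figures seen (omnibus 9.9% with ATE weights and 17.9% with ATT weights) needed eight covariates and strong selection, which the documents do not indicate.

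All sizes rest on the assumed settings above, and mothers' outcomes were not simulated. The finding concerns weighted GEE results only. It is worth correcting but does not by itself overturn any conclusion.

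**What to change.** 1. Remove or correct the statement that the sandwich accounts for score estimation. State the weight type, the score covariates (including whether each outcome's baseline value is one), and whether the omnibus test is weighted.
2. For any weighted GEE, take standard errors, intervals and the group-by-time test from a bootstrap that resamples participants with all their visits together and refits the propensity model and weights each time, with at least 1,000 resamples.
3. Use a small-sample reference: t(N−2) for single contrasts; for the omnibus Wald statistic W, refer W(N−4)/(3(N−2)) to F(3, N−4), with N the participants in that model. At N = 80 this is W × 76/234 on F(3, 76), so the 5% limit for W is 2.725 × 234/76 = 8.39, against 7.81 on chi-square. With completely random dropout from 100 to 80 this held 5.0–5.9%.
4. Do not substitute an uncorrected stacked sandwich at about 40 per group. If a corrected joint-estimation variance was in fact used, say so instead.

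**Cost.** SAP wording and computing time; no new data. Nominal power falls where the usual test was liberal: with eight covariates, strong selection and ATE weights, 70.9% against 85.3%, at type I error 3.6% against 9.9%. Intervals can be slightly conservative (single-contrast error down to 1.9% with ATT weights). Using the bootstrap within each of the 20 imputed sets and combining by Rubin's rules is a natural extension but is untested. Because the SAP is written in the past tense, refitted results should be labelled as a correction made after the analysis and shown beside those already obtained.
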